11.2 Safety Laboratory Assessments

Blood and urine samples will be collected at the time points specified in the Schedule of Events (refer to the Protocol) to conduct hematology, chemistry, and urinalysis (including microscopic examinations) analyses. Clinical laboratory data will be summarized by the type of laboratory test. The number and percentage of subjects who experience abnormal (i.e., outside of reference ranges) and/or clinically significant abnormalities after study drug administration will be presented for each clinical laboratory

measurement. For each clinical laboratory measurement, descriptive statistics will be provided for baseline and all subsequent post-treatment scheduled visits.

Changes from baseline to the post-treatment visits will also be provided. Descriptive statistics of vital signs will also be provided in a similar manner. In addition, shift from baseline in CTCAE grade (where applicable) and by high/low flags (where CTCAE grades are not defined) will be presented by dose level.

The following tests will be performed within each of the specified test panels:

Hematology:	Serum Chemistry:	Urinalysis & Microscopic Urinalysis:

 RBC ($\times 10^{12}/L$) 	
 ALT (U/L) 	
 pH (4.5-8)

 WBC with differential (% and absolute; $\times 10^9/L$) 	
 Albumin (g/L) 	
 Specific gravity (1.002-1.030)

 Hemoglobin (g/L) 	
 Alkaline phosphatase (U/L) 	
 Protein (g/L)

 Hematocrit (L/L) 	
 Lipase (U/L) 	
 Glucose (mmol/L)

 Platelets ($\times 10^9/L$) 	
 AST (U/L) 	
 Blood

 PT/INR 	
 Total bilirubin ($\mu\text{mol}/L$) 	
 Nitrite
	
 Direct bilirubin ($\mu\text{mol}/L$) 	
 Microscopic Analysis (only if positive dipstick results):
	
 Total protein (g/L) 	
 RBC/high power field
	
 Creatinine ($\mu\text{mol}/L$) 	
 WBC/high power field
	
 BUN/Urea (mmol/L) 	
 Epithelial cells, casts etc
	
 Creatine kinase (U/L) 	
	
 GGT (U/L) 	
	
 Potassium (mmol/L) 	
	
 Sodium (mmol/L) 	
	
 Glucose (mmol/L) 	
	
 Chloride (mmol/L) 	
	
 Bicarbonate (mmol/L) 	

	
 • Calcium (mmol/L) 	
--	--	--

All laboratory data collected at scheduled and unscheduled visits will be included in the listings, but only results collected as scheduled visits will be included in the summary tables.

If required, the results (and the corresponding normal range cut-off values) for individual parameters may be converted to International System of Units (S.I.) units to summarize the data.

For all the parameters where a unit value has been reported, the parameter names that will be used in the outputs will comprise of the test name and the unit of measure, for example, 'Albumin (g/L)'. For the urinalysis parameters, the parameter name will be the reported test name only. Parameters will be sorted alphabetically within tables and listings.

For all parameters where a normal range limit value was reported, the normal range will be derived based on the available lower and upper limit values and any reported mathematical symbols. If both a lower and upper limit value is available, the normal range will be presented as '(Lower, Upper)'

The reported results for each parameter with a defined normal range will be classified ('Low', 'Normal', 'High') in relation to the defined normal range limits. If a result is equal to the normal range cut-off value, the result will be considered 'Normal'.

The hematology and chemistry results tables will present summary statistics for each laboratory parameter within the specific test panel. For each parameter, summaries will be presented for the baseline and each scheduled post-baseline visit. In addition, summaries will be presented for the change from baseline values at each scheduled post-baseline visit (continuous descriptive analysis).

In particular, quantitative data will be summarized using simple descriptive statistics (mean, SD, median, minimum, and maximum) of actual values and changes from baseline for each nominal visit over time. The changes computed will be the differences from baseline. Qualitative data based on reference ranges will be described according to the categories (i.e., Low, Normal, High).

The decimal precision to which the summaries for each parameter will be based on the maximum number of decimals to which the reported result or the normal range limits are presented to in the raw data. The results and normal ranges will be displayed to the same decimal precision in the listings.

Additionally, counts (%) of number participants with values out of normal range at each scheduled time point will also be presented along with shift tables that will represent the changes in normal range categories across post-baseline time points (categorical descriptive analysis).

The urinalysis table will present counts and percentages of normal, abnormal clinically significant and clinically significant for the reported results at baseline and each post-baseline visit for all parameters (categorical descriptive analysis).

11.3 Vital Signs

The following vital signs measurements will be taken at the time points specified in the Schedule of Events (refer to the Protocol):

- Pulse (beats/min);
- Systolic Blood Pressure (SBP) (mmHg)
- Diastolic Blood Pressure (DBP) (mmHg)
- Respiratory Rate (breaths/min)
- Body Temperature (°C)

All vital signs data collected at scheduled and unscheduled visits will be included in the listings, but only results collected as scheduled visits will be included in the summary tables.

Triplicate orthostatic vital signs (blood pressure and heart rate) will be recorded at baseline (Check-in Day -1) 15 minutes apart (the average will be used to determine eligibility).

The parameter names that will be used in the outputs will comprise of the test name and the unit of measure, for example, 'Systolic Blood Pressure (mmHg)'. Parameters will be sorted in the order that the measurements were collected in on the Vital Signs eCRF page within the tables and listings.

Vital signs measurements will present summary statistics for the results at the baseline and each scheduled post-baseline visit for each of the parameters in Supine and Standing position. In addition, summaries will be presented for the change from baseline values at each scheduled post-baseline visit in Supine and Standing position (continuous descriptive analysis). The average of triplicate vital signs in Supine and Standing position will be used as baseline for HR and BP.

In addition, vital signs and postural changes, the individual subject level at each time point between the two positions in which readings are taken (Supine vs Standing) will be reported. At each timepoint standard descriptive stats for HR, sBP and dBP postural data will be reported.

Further, a categorical tabulation for number (percentage) of subjects per time point (and overall categories for any post-exposure timepoint for each parameter separately and for the 2 BP measures together) for the following clinically changes will be created:

- Drop in dBP of ≥ 10 mmHg when moving from supine to standing
- Drop in sBP of ≥ 20 mmHg when moving from supine to standing
- Increase in HR of ≥ 30 bpm when moving from supine to standing

The decimal precision to which the summaries for each parameter will presented will be based on the maximum number of decimals to which the results were reported on the eCRF.

11.4 12-Lead Electrocardiogram (ECG)

The following ECG measurements will be taken at the time points specified in the Schedule of Events (refer to the Protocol):

- Heart Rate (bpm)
- QT interval (msec)
- PR interval (msec)
- QRS interval (msec)
- RR Interval (msec)
- QTcF (msec)
- QTcB (msec)
- ECG clinical interpretation

All ECG data collected at scheduled and unscheduled visits will be included in the listings, but only results collected as scheduled visits will be included in the summary tables.

The parameter names that will be used in the outputs will comprise of the test name and the unit of measure, for example, 'Ventricular Rate (beats/min)'. Parameters will be sorted in the order that the measurements were collected in on the ECG eCRF page within the tables and listings.

ECG measurements will present summary statistics for the results at the baseline and each scheduled post-baseline visit for each of the parameters. In addition, summaries will be presented for the change from baseline values at each scheduled post-baseline visit (continuous descriptive analysis). The average of the replicate measurements should be determined after the derivation of the individual parameter at each time point.

If multiple tracings are done as part of one assessment, the mean of the three tracings per parameter and the worst clinical interpretation per timepoint will be summarized for each participant. All values will be listed including the mean value per parameter and the worst clinical interpretation. Changes from baseline will be calculated based on the mean values of the triplicates where appropriate. The summary of overall interpretation findings table will present counts and percentages for the reported results at baseline and each post-baseline visit/time point. Result categories will be ordered as 'Normal', 'Abnormal Not Clinically Significant (NCS)' and 'Abnormal Clinically Significant (CS)' (categorical descriptive analysis).

The decimal precision for each parameter will be based on the maximum number of decimals to which the results were reported on the eCRF.

11.5 CV Telemetry

By-participant data listings will be created for CV Telemetry at all time points collected in CRF.

11.6 Neurological Exam

By-participant data listings will be created for all Neurological examination parameters at all time points collected in CRF.

11.7 Physical Examinations

By-participant data listings will be created for all physical examination parameters at all time points collected in CRF

12. CHANGES TO THE PLANNED ANALYSIS

Changes to planned analysis include:

- The following endpoint has been added in relation to PK analysis: To potentially identify significant difference between gender of PK parameters in plasma.
- Standard descriptive stats for HR, sBP and dBP postural data will be reported using a categorical tabulation for number (percentage) of subjects per time point in relation to:
 - Drop in dBP of ≥ 10 mmHg when moving from supine to standing
 - Drop in sBP of ≥ 20 mmHg when moving from supine to standing
 - Increase in HR of ≥ 30 bpm when moving from supine to standing
- For triplicate vital sign at Day -1/ baseline average value will be used.
- Pharmacodynamic Exploratory Endpoints will not be included in the SAP.
- To date, RNA/DNA Analysis has not been conducted, and no data is available for the SAP.
- No suicidal assessments were conducted as part of this study; therefore, this will not be included in data listings.
- It was decided that screen failure data will not be entered in the EDC, as it is the site/CRO practice for phase 1 studies because there are hundreds of SFs, and this data is not imperative for any analysis.

- **INTERIM AND FINAL ANALYSIS**

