3.3 Inferential Analyses

Descriptive statistics will be used to summarize the safety and PK data. No formal hypothesis testing is planned.

All analyses (unless otherwise specified) will be performed at a two-sided 10% level of significance.

- Dose Proportionality

Dose proportionality will be evaluated for C_{max} , AUC_{inf} , AUC_t , AUC_{24} (SAD) and steady state parameters AUC_{tau} and $C_{max,ss}$ (MAD). Data will be presented graphically and a statistical analysis using the power model will be conducted. The analysis will be divided into days:

SAD: C_{max} , AUC_{24} , AUC_t , AUC_{inf}

MAD Day 1: C_{max} , AUC_{24}

MAD Day 7: $C_{max,ss}$, AUC_{tau} .

The model will include the \log_e -transformed CVN766 dose level as an independent variable. This model will be used to investigate the null hypothesis ($H_0: \beta=1$). Dose proportionality will be rejected ($H_1: \beta$ not equal 1) if the 90% CI of the estimated slope falls outside the critical interval.

The power model will have the form:

$$Y = a*(dose)^b$$

where Y is the PK parameter, and a and b are the coefficient and exponent, respectively, of the power equation.

By taking the natural logarithm (ln), the power model can be analyzed using linear regression and has the form:

$$\ln(Y) = \ln(a)+b*\ln(dose) + error = \alpha + \beta*\ln(dose) + error,$$

where α is the intercept, and β is the slope, and $\ln(dose)$ is based on the dose size for each subject. Estimates of slope and intercept along with their 90% confidence intervals will be reported. A minimum of 3 values per dose must be available for a given parameter to estimate dose proportionality using the power model. For dose proportionality, the slope of the regression line (b) = 1 and for dose independence $b = 0$.

Apparent dose linearity and proportionality of PK Parameters will be assessed graphically as well. The scatter plots and power model regression line will be plotted together with the natural log-transformed PK parameters as the values on the y-axis, and the natural log-transformed dose level as the values on the x-axis. Regression/scatter plot for SAD and MAD in the log-log scale for the Hummel power analysis will be performed by day.

- Food Effect

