The effect of fed/fasting state on PK and bioavailability of CVN766 will be analyzed. The analysis will be descriptively. In addition, a random effects mixed model on the log-transformed pharmacokinetic parameters (AUC_t , AUC_{inf} , AUC_{24} , and C_{max}) will be applied to explore the effect of food, where meal status (fed vs. fasted) will be included as a fixed effect and participant will be included as a random effect. The geometric mean for fed/fasted and their 90% CIs will be estimated from the model based on the least squares means. The ratio of the geometric means (geometric mean ratio) and its 90% CI of the

fed data compared to the fasted data will be obtained based on the exponential of the difference of least-squares means (LSM) from the model.

- Gender Effect

The effect of gender (male vs. female) on Dose Normalized PK parameters of CVN766 will be analyzed. A random effects mixed model on the log-transformed pharmacokinetic parameters:

SAD: C_{\max}/Dose , AUC_{24}/Dose , AUC_t/Dose , $AUC_{\text{inf}}/\text{Dose}$ and $t_{1/2z}$

MAD Day 1: AUC_{24}/Dose , C_{\max}/Dose , AUC_t/Dose , $t_{1/2z}$ and t_{\max} .

MAD Day 7: $C_{\max,ss}/\text{Dose}$, $AUC_{\text{tau}}/\text{Dose}$, AUC_t/Dose , $t_{1/2z}$ and t_{\max} .

will be applied to explore the effect of gender, where gender (male vs. female) will be included as a fixed effect and participant will be included as a random effect. The geometric mean for Male/Female and their 90% CIs will be estimated from the model based on the least squares means. The ratio of the geometric means (geometric mean ratio) and its 90% CI of the Male data compared to the Female data will be obtained based on the exponential of the difference of least-squares means (LSM) from the model.

Point estimates and 90% CIs for differences on the log scale will be exponentiated to obtain estimates for the ratios of geometric means and respective 90% CIs on the original scale.

For $t_{1/2z}$, a non-parametric analysis (Hodges-Lehmann estimate) will be used to produce the median difference between female and male. A p-value will be generated by the Wilcoxon signed-rank test.

3.4 Multiple Comparisons and Multiplicity Adjustments.

Not applicable for this study.

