Inferential Analyses

The following endpoints will be analyzed as described in [sections 3.3](#):

- Dose proportionality
 - Dose proportionality - CVN766 SAD
 - AUC_{inf}
 - AUC_t
 - AUC_{24}
 - C_{max}
 - Dose proportionality - CVN766 MAD
 - MAD Day 1: C_{max} , AUC_{24}
 - MAD Day 7: $C_{max,ss}$, AUC_{tau}

- Food-Effect Assessment (SAD: Cohort S3):

The following parameters will be analyzed as described in [sections 3.3](#):

- AUC_t
- AUC_{inf}
- AUC_{24}
- C_{max}

- Gender effect Assessment

The following parameters will be analyzed as described in [sections 3.3](#):

SAD : $C_{max}/Dose$, $AUC_{24}/Dose$, $AUC_t/Dose$, $AUC_{inf}/Dose$, T_{max} and $t_{1/2z}$.

MAD Day 1: $AUC_{24}/Dose$, $C_{max}/Dose$, $AUC_t/Dose$, $t_{1/2z}$ and t_{max} .

MAD Day 7: $C_{max,ss}/Dose$, $AUC_{tau}/Dose$, $AUC_t/Dose$, $t_{1/2z}$ and t_{max} .

Details are provided in [section 3.3](#) of SAP.

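### The SAP adds a search for significant gender differences in PK, over 15 or 16 unadjusted comparisons at the 10% level, while stating that no formal testing is planned

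*SAP*

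**What the plan says.** Section 12 of the SAP records a new endpoint for plasma PK: "To potentially identify significant difference between gender of PK parameters in plasma". Gender does not appear among the objectives (section 2.2) or the endpoints (section 2.3), so section 12 is where it enters the plan.

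Section 3.3 opens with "No formal hypothesis testing is planned" and then sets a default: "All analyses (unless otherwise specified) will be performed at a two-sided 10% level of significance". The Gender Effect paragraph does not opt out of that default. It describes a log-scale model that "will be applied to explore the effect of gender, where gender (male vs. female) will be included as a fixed effect", with geometric mean ratios and 90% CIs. For t1/2z it adds a Hodges-Lehmann difference and says "A p-value will be generated by the Wilcoxon signed-rank test". Section 3.4, on multiplicity, reads in full "Not applicable for this study".

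Section 3.3 lists 5 SAD, 5 MAD Day 1 and 5 MAD Day 7 parameters. Section 10.7 and shells 14.2.8.1 and 14.2.8.2 list 6, 5 and 5; the extra one is SAD Tmax.

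**The concern.** The document gives two incompatible accounts of one analysis. In one, gender is explored by estimation and multiplicity has no bearing. In the other, the purpose is to find significance, a 10% level applies by default, and one parameter gets a p-value. Nothing says which account governs, which parameter, part or day would settle whether there is a gender effect, or how many intervals excluding no difference would count.

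What is at stake is the wording that the CSR may use. Under the second account, any one of 15 or 16 intervals could be reported as a significant gender difference in PK. AUC, Cmax, Tmax and half-life, or SAD and MAD, could disagree with no rule for choosing between them.

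The SAP's labelling safeguards do not resolve this. Section 1 requires post hoc or unplanned exploratory analyses to be identified as such in the CSR, and section 4 does the same for exploratory analyses not identified in the SAP. The gender analysis is identified in the SAP, so neither applies, and the titles of the two gender tables carry no exploratory label.

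**Working it through.** The SAP states no error rate for this analysis, so there is no figure to reproduce. The check asks how often at least one comparison would exclude no difference if gender had no effect.

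**Inputs from the SAP**
- Comparisons: 5 + 5 + 5 = 15 (section 3.3) or 6 + 5 + 5 = 16 (section 10.7 and the shells).
- Level: two-sided 10% per comparison (section 3.3). A 90% CI that excludes a ratio of 1, or a difference of 0, is equivalent to this.
- Active participants: SAD 5 × 6 = 30, MAD 3 × 6 = 18 (section 2.5). The section 2.4 total of 64 = 40 + 24 implies different people in the two parts, so SAD and MAD results are independent.

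**Assumptions**
- Correlation between parameters, which the SAP does not give.
- Gender split: 15/15 and 9/9, with 22/8 and 13/5 as a check.
- A t-test stands in for the Hodges-Lehmann comparison, whose interval is taken at 90%.

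**Independent comparisons.** P(at least one) = 1 − 0.9^k. For k = 16 this is 1 − 0.9^16 = 0.815; for k = 15 it is 1 − 0.9^15 = 0.794.

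**Correlated comparisons.** Simulation of 40,000 null trials, k = 16, with the same correlation between all parameters within a part (MAD Day 1 and Day 7 together):

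| Assumed correlation | SAD (6) | MAD (10) | All 16 |
|---|---|---|---|
| 0 | 0.465 | 0.652 | 0.815 |
| 0.5 | 0.377 | 0.493 | 0.686 |
| 0.8 | 0.255 | 0.314 | 0.489 |
| 0.9 | 0.201 | 0.237 | 0.389 |
| 0.95 | 0.170 | 0.191 | 0.329 |

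Repeat runs gave 0.683 at 0.5, 0.527 at 0.75 and 0.491 at 0.8, so the probability crosses one half between 0.75 and 0.8.

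A structured pattern was also tried: AUCs correlated 0.95 to 0.99 with each other, Cmax with AUC 0.7 to 0.9, t1/2z and Tmax 0 to 0.4 with the rest, Day 1 with Day 7 0.7 to 0.95. It gave 0.53 to 0.67. The uneven gender split moved results by at most about 1 percentage point.

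**Floor.** Each part has at least a 10% chance of one exclusion, and the parts are independent. Perfect correlation within each part therefore gives 1 − 0.9² = 0.19.

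**Expected count.** 16 × 0.10 = 1.6 false exclusions (15 × 0.10 = 1.5), whatever the correlation.

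**The case against.** The strongest reply is that this is an exploratory Phase 1 comparison. Section 3.3 disclaims formal testing and uses the verb explore, and section 2.4 gives no sample size calculation for the same reason. On that footing unadjusted 90% CIs are ordinary practice, and a multiplicity section that says nothing is needed is coherent. The only gender p-value named is for t1/2z, and the shells have no p-value row. No sentence says that a gender interval excluding 1 counts as an effect, whereas dose proportionality does get a null hypothesis and a rejection rule. The family of 16 tests therefore has to be inferred from the endpoint wording and the default 10% level.

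Much of that stands. Leaving an exploratory analysis unadjusted is not the fault, and adding gender in section 12 is properly disclosed. What the reply does not remove is an endpoint defined as identifying a significant difference, under a default significance level from which the gender analysis is not exempted.

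A reader might also infer that a false gender effect is more likely than not. The documents do not support that. It depends on correlations that the SAP does not give, and it fails at a uniform within-part correlation of about 0.8 or more. High correlation is plausible for much of the list: the AUCs come from the same curves, MAD Day 1 sampling stops at 24 hours so AUCt and AUC24 nearly coincide there, and Day 1 and Day 7 share participants.

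**Conclusion.** The contradiction is real and worth correcting. If an interval excluding no difference is read as a significant gender effect, the chance of at least one among 16 with no true effect is 81% under independence, about 39% to 69% at within-part correlations of 0.9 to 0.5, and never below about 19%, against a nominal 10%. Inflation holds at every correlation; its size is conditional on assumed values. The figures also depend on reading the section 12 wording and the default level as a decision rule, which the SAP neither confirms nor rules out. The point is that the plan should say which it means.

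**What to change.** 1. Section 12: reword the endpoint as an exploratory, estimation-only assessment of plasma PK by gender, with no claim of significance.
2. Section 3.3, Gender Effect: state that the 90% CIs are for estimation and unadjusted, and exempt this analysis from the 10% significance sentence. Leave that sentence in place otherwise; deleting it outright would also touch the dose-proportionality rule.
3. Section 3.3: delete the gender p-value. This also removes the Wilcoxon signed-rank test, a paired test that does not fit independent male and female groups. Keep the Hodges-Lehmann difference with its 90% CI, after reconciling whether it applies to t1/2z (section 3.3) or Tmax (table shells). Align the SAD list with section 10.7 at the same time.
4. Section 3.4: replace the current entry with a statement that no adjustment is made and that no single gender interval supports a claim of a gender difference.

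The cost is SAP wording and the removal of one p-value. No data, participants, estimates or intervals are lost. The downside is that the CSR can no longer call a gender difference significant.
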